#### 6.1.4. Types of adverse events

Expected adverse event: Risks or events reported in the literature for moxidectin and/or ivermectin.

Unexpected adverse event: An unexpected event is any AE that is not identified in nature, severity, or frequency in the scientific literature.

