#### 6.1.3. Relatedness

Relatedness will be assessed as defined below based on the temporal relationship between the AE and the treatment, known side effects of treatment, medical history, concomitant medication, course of the underlying disease and trial procedures.

Possibly related: an AE which can medically (pharmacologically/clinically) be attributed to the study treatment.

Unrelated: an adverse even which is not reasonably related to the study treatment. A reasonable alternative explanation must be available.

An AE that is determined to be related to the administration of a study product is referred to as an "adverse drug reaction."

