#### 6.1.6. Suspected unexpected serious adverse reactions

A suspected unexpected serious adverse reaction (SUSAR) is an unexpected adverse drug reaction which also meets the definition of serious adverse events.

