#### 6.2. Methods of recording and assessing adverse events

Patients will be kept for observation for at least 3 hours following each morning treatment for any acute AEs. During the reporting period, any unfavorable changes in the subject's condition will be recorded as adverse events, whether reported by the subject or observed by the investigator. In case of any abnormal finding, the local study physician will perform a full clinical examination and findings will be recorded. An emergency kit will be available on site to treat any medical conditions that warrant urgent medical intervention.

In addition, patients will be also interviewed by a nurse and/or a physician about the occurrence of AEs 24 hours after treatment.

Information on all AEs (onset, duration, intensity, seriousness and causality) will be immediately entered in the appropriate AE module of the CRF which is considered as a source document. For all AEs, sufficient information will be pursued and/or obtained so as to permit i) an adequate determination of the seriousness of the event (i.e. whether the event should be classified as a SAE); ii) an assessment of the casual relationship between the AE and the study treatments (i.e. whether the event should be classified as an adverse drug reaction); and iii) an assessment of intensity of AEs by the study physician.

All SAE, unexpected adverse drug reactions, or SUSARs must be reported as described in Section 6.3.

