#### 6.3. Reporting of serious adverse events

Any study-related unanticipated problem posing risk of harm to subjects or others, and any type of serious adverse event, will be reported (within 24h between site's knowledge about the event and notification) to

[name]. [name] (principal investigator) Swiss Tropical and Public Health Institute, [contact] [contact] E-mail: [contact]

Page 30 of 45

Within the following 48 hours, the local co-investigator must provide to study sponsorinvestigator further information on the serious adverse effect or the unanticipated problem in the form of a written narrative. This should include a copy of a completed SAE form, and any other diagnostic information that will assist the understanding of the event. In exceptional circumstances, a serious adverse event may be reported by telephone. In these cases, a written report must be sent immediately thereafter by fax or e-mail. Names, addresses and telephone for serious adverse event reporting will be included in the trial-specific SAE form. Relevant pages from the CRF may be provided in parallel (e.g., medical history, concomitant medications).

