#### 6.4. Safety reporting to Health Authorities and Ethics Committees

The sponsor-investigator will send appropriate safety notifications to Health Authorities in accordance with applicable laws and regulations. Additionally, this information will be provided to the 'Ethik Kommission Nordwest- und Zentralschweiz' (EKNZ, Switzerland) and the ethic committee of Lao PDR according to national rules. Fatal or life-threatening serious adverse events or SUSARs will be reported within 24 hours (between sponsor-investigator's knowledge about the event and notification) followed by a complete report within 7 additional calendar days. Other serious adverse events and SUSARs that are not fatal or life-threatening will be filed as soon as possible but no later than 14 days after first knowledge by the sponsor-investigator.

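### Section 6.1.4 judges expectedness against moxidectin and ivermectin literature together, so an ivermectin-only reaction in a moxidectin recipient can miss the unexpected-reaction class or the SUSAR label

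*Combined protocol and SAP*

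**What the plan says.** Section 6.1.4 gives two definitions. An expected event is "Risks or events reported in the literature for moxidectin and/or ivermectin". For the opposite class, "An unexpected event is any AE that is not identified in nature, severity, or frequency in the scientific literature". Neither sentence refers to the product that the participant took. No section names a label, brochure or event list as the reference for either drug.

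Three later provisions use these definitions:

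- Section 6.1.3: "An AE that is determined to be related to the administration of a study product is referred to as" an adverse drug reaction.
- Section 6.1.6: a SUSAR "is an unexpected adverse drug reaction which also meets the definition of serious adverse events".
- Section 6.2: "All SAE, unexpected adverse drug reactions, or SUSARs must be reported as described in Section 6.3".

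For serious events there are separate rules that do not look at expectedness. Section 6.3 sets the site's duty towards the principal investigator: "any type of serious adverse event, will be reported (within 24h between site's knowledge about the event and notification". Section 6.4 sets the duty towards authorities and ethics committees: "Fatal or life-threatening serious adverse events or SUSARs will be reported within 24 hours", and "Other serious adverse events and SUSARs that are not fatal or life-threatening will be filed as soon as possible", with a limit of 14 days.

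**The concern.** Expectedness is meant to separate what is already known about a product from what is new. A reference set that joins two products cannot do this for either one. A reaction never described for moxidectin stops being new as soon as it has been described for ivermectin.

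Safety and tolerability of moxidectin are secondary objectives in both trials (section 3), and section 2 calls the existing safety evidence insufficient. Section 11.2 provides for no data and safety monitoring board, so case-level classification is one of the ways in which a new reaction would be noticed. What is at stake is the classification of individual reactions and one reporting class. The safety dataset itself is not at stake.

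**Working it through.** The plan gives no figure to reproduce, so the check is to follow the definitions through to the reporting rules.

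**Step 1: the two reference sets.** Let M be the reactions whose nature, severity and frequency are described for moxidectin, and I the same for ivermectin. Read literally, section 6.1.4 makes the expected set M ∪ I for every participant. Judged by product received, the expected set for a moxidectin recipient would be M. The two differ by I \ M, the reactions described for ivermectin only.

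| Reaction described for | Section 6.1.4 read literally | Judged for a moxidectin recipient |
|---|---|---|
| both drugs | expected | expected |
| moxidectin only | expected | expected |
| ivermectin only | expected | **unexpected** |
| neither drug | unexpected | unexpected |

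M is contained in M ∪ I, so the pooled rule can take a reaction out of the unexpected class but can never add one. For an ivermectin recipient in trial B the same holds with the drugs exchanged.

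**Step 2: what depends on the label.** Take a related reaction from the third row.

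| | Serious | Non-serious |
|---|---|---|
| Recorded in the CRF (sections 6.1, 6.1.1, 6.2) | yes | yes |
| Sent to the principal investigator within 24 h (section 6.3) | yes, as an SAE | only if it counts as an unexpected reaction (section 6.2) or as an unanticipated problem posing risk of harm (section 6.3) |
| Sent to authorities and ethics committees (section 6.4) | yes, on the clock that SUSARs have | not named there |
| Puts the study on hold (section 5.4) | yes, for any SAE | no |
| Counts in the adverse event analysis (section 7.3) | yes | yes |
| Effect of being called expected | SUSAR label lost | section 6.2 reporting class missed |

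**Step 3: trial A.** Its seven arms are six moxidectin doses and placebo (section 4.3). Ivermectin is given only at the end, to placebo recipients and to those still positive (sections 4.3.4, 4.4 and 9.6), and not as study treatment. Section 4.2 lists participants and laboratory technicians as the blinded parties. Moxidectin is the only active study product, so there is no second product to pool with and blinding gives no reason to do so.

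**Step 4: size.** With 30 participants per arm in trial A and 175 per arm in trial B (section 7.2), planned moxidectin recipients number 6 × 30 + 175 = 355 of 210 + 350 = 560, and 355/560 = 63%. This is the population in which the third row could apply. It does not count or estimate affected events. That would need the membership of I \ M and the rates of those reactions, and the documents give neither.

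**The case against.** The strongest reply is that almost nothing depends on the label. Serious events go out within the same limits whether or not they are SUSARs, the study hold in section 5.4 is triggered by any SAE, every adverse event is recorded, and section 7.3 compares proportions without using expectedness. All of this stands. A reader might infer that serious moxidectin reactions would go unreported or be reported late, or that the safety comparison would be biased. The documents do not support either inference.

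The non-serious route is also thin. Section 6.2 refers to section 6.3, but section 6.3 describes only SAEs and unanticipated problems posing risk of harm. It gives non-serious unexpected reactions no procedure or clock of their own, and section 6.4 does not name them. Some could still be caught as unanticipated problems. This stands too: the loss is at most a notice to the principal investigator. Section 6.2 nonetheless makes that notice mandatory, and whether something is an unanticipated problem is a matter of judgement.

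Section 2 describes the two drugs' clinically significant adverse events as very similar, and section 6.1 lists the common ones jointly. This makes the set I \ M likely to be small, but it does not make it empty. Section 2 also reports a lower neurotoxic potential, a much longer half-life and a larger volume of distribution for moxidectin. An event more severe or more frequent than described can still be unexpected under section 6.1.4, but that comparison is again with literature on no stated product.

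Finally, *and/or* may have been meant as *for the respective product*. That reading is possible, but nothing in the text establishes it. The double blind could explain pooling in trial B but not in trial A.

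**Conclusion.** The point holds as a minor defect of definition. Read literally, section 6.1.4 classes an ivermectin-only reaction as expected in a moxidectin recipient, and the error can run in only one direction. Its reach is limited to two things: non-serious reactions that miss the reporting class in section 6.2, and serious ones that lose the SUSAR label of section 6.1.6 while still being reported on time.

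The conclusion assumes the literal reading of *and/or*. It also has practical effect only if at least one reaction matches the ivermectin literature in nature, severity and frequency and is not described for moxidectin. The documents neither identify such a reaction nor rule one out. A reader might take the 63% who receive moxidectin as the scale of the problem. It is not, because the number of affected events cannot be derived.

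**What to change.** Reword section 6.1.4 so that an event is expected only if its nature, severity and frequency are described in a named reference source for the study product received, and name one such source for each product. Without a named source, the reworded rule would still leave open which literature counts.

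- **Trial A:** judge against the moxidectin source only.
- **Trial B, while the blind holds:** judge against each source separately, and handle the event as unexpected if it is unexpected for either product. In the notation above, only M ∩ I then counts as expected, so nothing new for the drug taken is missed and no unblinding is needed.

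The change takes a sentence or two and leaves sample size, analysis and clinical management as they are. The price is some over-reporting in trial B: reactions already known for the drug actually taken, but not for the other, will be handled as unexpected. The documents give no basis for saying how many.

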#### 6.1.5. Serious adverse events

According to the ICH "Clinical Safety Data Management: Definitions and standards for expedited Reporting E2A"

(https://www.ich.org/fileadmin/Public Web Site/ICH Products/Guidelines/Efficacy/E2A/Step 4/E2A Guideline.pdf) a serious SAE includes any event (experience) or reaction in any untoward medical occurrence that at any dose:

- 1. is fatal, results in death;
- 2. is life threatening, meaning, the subject was, in the view of the investigator, at immediate risk of death from the reaction as it occurred, i.e., it does not include a reaction that, had it occurred in a more serious form, might have caused death;
- 3. is a persistent or significant disability or incapacity, i.e., the event causes a substantial disruption of a person's ability to conduct normal life functions;
- 4. requires, or prolongs in-patient hospitalization;
- 5. is a congenital anomaly or birth defect;
- 6. is an important medical event, based upon appropriate medical judgment, that may jeopardize the patient or subject or may require medical or surgical intervention to prevent one of the other outcomes defining serious.

A "severe" AE does not necessarily meet the criteria for a "serious" AE. Serious adverse events are reported from the first dose of study medication to 21 days post-treatment.

SAEs that are still ongoing at the end of the study period will be followed up to determine the final outcome. Any SAE that occurs after the study period and is considered to be possibly related (definitions will be used according to the WHO-UMC system; see: http://who-umc.org/Graphics/24734.pdf) to the study treatment or study participation will be recorded and reported immediately.

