Measurements & procedures	Three stool samples will be collected at baseline if possible on three consecutive days or otherwise within a total maximum of 6 days and analysed by a quantitative Baermann method (in duplicates) for S. stercoralis infection. Co-infection with T. trichiura, A. lumbricoides and hookworm infection will be identified using duplicate Kato-Katz thick smears on stool samples from two consecutive days. The medical history of the participants will be assessed with a standardized questionnaire, in addition to a clinical and physical examination carried out by the study physician shortly before treatment day. The adults will also be interviewed before treatment, 3 and 24 hours as well as 28 days after treatment about the occurrence of AEs. The efficacy of the treatment will be determined 21-28 days post-treatment by collecting another three stool samples. All stool samples will be examined with duplicate Baermann assays and Kato-Katz thick smears and recorded quantitatively. A subsample of adults will further be sampled using finger pricking for micro sampling at 0, 2, 4, 8, 24, and 72 hours, 7 and 28 days post treatment to evaluate pharmacokinetic parameters (trial A). For validation of the analytical method the subsample of one study arm (8 mg, trial A) will undergo venous blood sampling in addition to finger pricking. To all participating households, a brief questionnaire will be administered assessing information on socioeconomic characteristics (possession of indicator assets) and access to sanitation, water facilities, and hygiene behaviour at first visit. Additionally, soil and water samples at different sites will be taken.
Statistical Analyses	An available case analysis (full analysis set according to the intention to treat principle) will be performed, including all subjects with primary end point data. Supplementary, a per-protocol analysis will be conducted. CRs will be calculated as the percentage of larvae-positive subjects at baseline who become larvae-negative after treatment. Larvae per gram (LPG) stool sample will be assessed by calculating the mean of the larvae counts from the three duplicate Baermann assays and divided by the mean weighted amount of these stool samples. The LRR will

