#### 4.3.3. Adverse effects assessment

All participants will be kept for observation for at least 3 hours following each morning treatment for any acute adverse events and additionally will be interviewed and examined about existing and emerging clinical symptoms (i.e. headache, abdominal pain, itching, nausea, vomiting, diarrhea, body temperature, and allergic reaction) before treatment (baseline examination), 3 hours, 24 hours and 28 days after treatment (adverse effects assessment) to determine the occurrence of AE (see chapter 6.2). Any symptoms will be recorded in the CRF and immediate action will be perused (see chapter 6).

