## 4.6. Schedule of visits

Table 1. Schedule of visits of DF (trial A) and parallel group (trial B) study.

Screening /					Follow up		
Time point	Day -28	Day -1-3	0 h	л	3 h	24 h	Day 28
Informed consent	х			ando			
Diagnosis (stool examination) (a)	х			Randomization			х
Questionnaire	х			on and			
Medical history (c)		х					
Clinical examination (d)		Х		ninistr			
Physical examination (e)		х		administration of			
Randomization administration of treatment			х				
Capturing AEs (f)				treatment	х	Х	х
Capturing SAE (f)				1t	х	х	х

(a) on three stool samples duplicate Baermann assays and on two stool samples duplicate Kato-Katz thick smears. (b) date of birth, age, sex, height, weight, body temperature, pulse rate, blood pressure, hb measurement, pregnancy test and recording of breastfeeding

(c) information gained by asking specific questions concerning chronic disease and concomitant medication.

(d) investigation for signs of disease: head ache, abdominal pain, nausea, vomiting, diarrhea, itching, other symptoms. (e) examination on ear, nose, throat, eyes, lungs, lymph nodes and skin.

(f) a standardized symptom questionnaire is used, that includes the recording of headache, abdominal pain, itching, nausea, vomiting, diarrhea, allergic reaction, others

(g) only in trial B

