# 6. Assessment of safety

### 6.1. Adverse event definition

Few adverse events have been reported following moxidectin or ivermectin administration in STH-infected individuals. The most common AEs were abdominal cramps, headache, nausea, diarrhea, fever and vertigo [11, 12, 36, 37].

The observation time for AE starts when the treatment is initiated. Subjects will be kept for observation for at least 3 hours following treatment for any acute AEs. If there is any abnormal finding, the local study physician will perform a full clinical examination and findings will be recorded. An emergency kit will be available on site to treat any medical conditions that warrant urgent medical intervention. Participants will also be interviewed 3, 24 hours, 28 days after treatment about the occurrence of AEs.

Information on all AE (incidence, onset, cessation, duration, intensity, frequency, seriousness and causality) will be entered immediately in the source document, and also in the appropriate AE module of the case report form. For all AEs, sufficient information will be pursued and/or obtained so as to permit i) an adequate determination of the outcome of the event (i.e. whether the event should be classified as a SAE); and; ii) an assessment of the casual relationship between the AE and the study treatments. Intensity of AE will be judged by the study physician, following guidelines by the European Medicine Agency (Note for Guidance on Clinical Safety Data Management).

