#### 6.1.2. Severity grading

Adverse signs or symptoms will be graded by the investigator as mild, moderate, severe or life threatening according to the following definitions (https://evs.nci.nih.gov/ftp1/CTCAE/CTCAE 4.03 2010-06-14 QuickReference 5x7.pdf).

Grade	Definition
1:	mild adverse events
2:	moderate adverse events.
3:	severe adverse events.
4:	life threatening or disabling adverse events.
5:	death related to adverse events.

The observation time for adverse events starts when the treatment is initiated and continues until 28 days post-treatment. For the purpose of this trial, disease progression and relapse will be considered as treatment failure, not as an AE.

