#### 10.1. Data collection

The data produced from this research project will fall into the following categories:

- 1. Eggs/Larvae counts of hookworm, *Ascaris lumbricoides* and *Trichuris trichiura* and *S. stercoralis* found in participants' stool, soil or water samples using either the Kato-Katz or the Baermann technique before (baseline; stool, soil, water) and after (follow-up; stool) treatment.
- 2. Personal information such as name, age and gender of trial participants.
- Anthropometric and clinical characteristics of the trial participants collected using the study's CRF such as weight, height, blood pressure, temperature, any abnormal medical condition or chronic disease.
- 4. Number and type of adverse events registered in the CRF and actively probed for 3 and 24 hours after treatment. The same data will be collected during the collection of the follow-up, 28 days after treatment.
- Pharmacokinetic parameters such as Cmax, AUC, or tmax analyzed from capillary or venous blood sampling at 0, 2, 4, 8, 24, and 72 hours, 7 and 28 days post dosing or in between 0 and 28 days post dosing.
- 6. Questionnaire: Record of the socioeconomic data of each participant's household

Data from categories 1-5 will be both paper-captured and directly into tablets using CommCare HQ (Digmagi, Inc., Cambridge, MA). CommCare HQ is a routine data management system ensuring complete, consistent and reliable data entry. For quality assurance error, range and consistency checks will assessed. 15% of data will be controlled by standard operating procedure, any discrepancies will be corrected by consulting the hard copy. If more than 1% of the double entered data display discrepancies, all data in categories 2-4 will be double entered by two independent people for quality assurance and verified as described.

Data entered into CommCare HQ databases will only be accessible to authorized personnel directly involved with the study by use of a password. It will directly be saved on the personal, password-protected laptop of one of the Co-PIs and uploaded to a server hosted at Swiss TPH, Basel. Data in category 1-4 will be saved both in .xlsx and .csv.

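### Section 6.1.5 ends SAE reporting at day 21, although adverse event observation and SAE capture run to day 28

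*Combined protocol and SAP*

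**What the plan says.** **SAE window.** Section 6.1.5 sets the limit: "Serious adverse events are reported from the first dose of study medication to 21 days post-treatment". It then adds a clause for later events: "Any SAE that occurs after the study period and is considered to be possibly related" to the treatment or to study participation is still to be recorded and reported.

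**Adverse event window.** Section 6.1.2 says: "The observation time for adverse events starts when the treatment is initiated and continues until 28 days post-treatment". The interviews agree with that:
- Synopsis: "as well as 28 days after treatment about the occurrence of AEs"
- Section 4.3.3: "3 hours, 24 hours and 28 days after treatment (adverse effects assessment"
- Section 6.1: "Participants will also be interviewed 3, 24 hours, 28 days after treatment about the occurrence of AEs"
- Section 10.1: "The same data will be collected during the collection of the follow-up, 28 days after treatment"

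Table 1 in section 4.6 has a separate row, "Capturing SAE (f", with three marks against the three follow-up columns: 3 h, 24 h and Day 28.

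**Reporting duty.** Section 6.2 sends every SAE to section 6.3, which requires notification within 24 hours. Section 5.4 suspends the study after any SAE, pending review. None of the three carries an end date.

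**Related date.** Section 4.3.4 places the efficacy stools at day 28. Its next paragraph dates the end of the study, and ivermectin for participants who are still positive, at day 21.

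**The concern.** The plan collects SAEs through day 28 under a reporting rule that ends at day 21. Take an unrelated SAE on day 24. Section 6.3 calls for a report within 24 hours; section 6.1.5 puts the event outside the reporting period. Two sites could handle the same event differently, and each could point to the protocol.

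The limit is an operative safety rule. Section 11.2 provides no data and safety monitoring board, and section 5.4 makes an SAE the trigger for pausing the study. What is at stake is uniform SAE reporting across sites, not the efficacy analysis.

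The day-21 date in section 4.3.4 is a second, smaller mismatch of the same kind: it does not fit the day-28 stools given in the same section.

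**Working it through.** The plan offers no figure to reproduce here. The check sets the dates side by side and then sizes the gap.

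**1. SAE dates**

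| Place | Rule | Last day |
|---|---|---|
| 6.1.5 | SAE reporting | 21 |
| 6.1.2 | Adverse event observation | 28 |
| 4.6, Table 1 | SAE capture | 28 |
| Synopsis, 4.3.3, 6.1, 10.1 | Adverse event interview | 28 |
| 5.4, 6.2, 6.3 | Action on or reporting of SAEs | none stated |

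The gap is 28 − 21 = 7 days (days 22 to 28), or 7/28 = 25% of the calendar days. This is not a share of expected events.

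**2. Which events are left in doubt**

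The general duty in 6.2 and 6.3 covers all SAEs. The late-event clause in 6.1.5 covers possibly related ones, though it starts only once the study period is over and 6.1.5 does not date that point. The events on which 6.1.5 pulls against 6.2 and 6.3 without any relief of its own are therefore chiefly unrelated SAEs on days 22 to 28.

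**3. Size, under assumed rates**

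Inputs: 210 participants (trial A) and 350 (trial B), with 10% loss, from section 7.2 and the synopsis. The SAE rates are assumptions.

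- Person-time = participants × 7 / 365.25.
- All enrolled: 210 + 350 = 560; 560 × 7 = 3,920 participant-days; 3,920 / 365.25 = 10.73 person-years.
- After 10% loss: 560 × 0.9 = 504; 504 × 7 = 3,528; 3,528 / 365.25 = 9.66 person-years.
- Trial B alone: 350 × 7 = 2,450; 2,450 / 365.25 = 6.71 person-years.

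Expected unrelated SAEs on days 22 to 28 = rate × person-years:

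| Assumed rate per 100 person-years | 560 enrolled | 504 after loss | Trial B, 350 |
|---|---|---|---|
| 1 | 0.11 | 0.10 | 0.07 |
| 5 | 0.54 | 0.48 | 0.34 |
| 10 | 1.07 | 0.97 | 0.67 |

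**4. The ivermectin date**

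Section 4.3.4 and Table 1 place the follow-up stools at day 28, section 5.5 dates the last stool examination at day 28 for trial A, and inclusion criterion 3 says about four weeks. Against these, day 21 is 28 − 21 = 7 days early. The synopsis and section 4.3 allow 21 to 28 days, and section 4.5 allows 3 to 4 weeks, so day 21 lies at the lower edge of that window. Even there it does not fit as an end of study: three stools on consecutive days from day 21 finish on day 21 + 2 = 23 at the earliest.

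**The case against.** **On SAE reporting.** Section 6.1.5 never says that SAEs after day 21 are not to be reported. A site that follows 6.2 and 6.3 would report a day-24 event whatever its cause, Table 1 prompts for it at Day 28, and section 5.4 would pause the study. This stands, and it is why the gap is confined mainly to unrelated events. It does not remove the contradiction, because an open-ended duty and a 21-day limit still apply to the same event. A reader might infer that serious events in the last week would go unreported; the documents do not support that.

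**On size.** The rates are assumed. Sections 3 and 4.3 already describe the 8 mg dose as resting on trial A, which suggests, without proving, that trial A dosing was over when this version was written. The trial B column may then be the relevant one. This also stands; the counts are small either way.

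**On ivermectin.** A reader might infer that ivermectin could be given before the endpoint stools and so distort the cure rate, above all in the placebo arm, where treatment does not depend on a positive stool and section 9.6 places it at the end of the study. The documents do not support this. Rescue goes only to those still positive, which requires the follow-up result first. Placebo participants are treated at follow-up under section 4.4, and sections 5.2 and 5.5 use that term for the stool visit at about four weeks, or day 28 in trial A. Section 5.5 bars other anthelmintics for everyone during the trial. No passage on placebo participants says day 21. What is left is a date to correct in 4.3.4.

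**Conclusion.** The inconsistency is real and minor. Section 6.1.5 contradicts section 6.1.2, Table 1 and the day-28 interviews by 7 days, and nothing in the plan resolves it. Its effect is limited mainly to SAEs judged unrelated on days 22 to 28. At assumed rates of 1 to 10 per 100 person-years, that is about 0.1 to 1.1 events over both trials, or 0.07 to 0.67 in trial B alone. These counts show scale only; the dates, not the counts, establish the point.

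The day-21 date in section 4.3.4 is a companion drafting error. No bias in cure rate or larvae reduction rate, no effect on power or alpha, and no ordering risk specific to the placebo arm is claimed.

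**What to change.** In section 6.1.5, change the end of SAE reporting from 21 to 28 days after treatment, to match section 6.1.2 and Table 1.

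In section 4.3.4, replace the bracketed day 21 with wording that ivermectin is given after the follow-up stool samples have been collected.

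Both are wording changes through the amendment route in section 8.1. The Day 28 visit, the interview and the SAE capture are already scheduled, so no visits, samples or participants are added.
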